9.4 Statistical methods

Biometric analysis will be defined in the statistical analysis plan which has to be authorized before closing the database by the biometrician, the sponsor, and the LKP.

OLD: Safety: The one-sided 97.5% confidence interval under H_0 for the difference of the event rates (rate in the CAS group – the rate in the CEA group) will be calculated. Non-inferiority is proven if the upper margin of this interval is less than 1.5%. This test has power of 90% if CAS shows a slight safety advantage compared to CEA (2.5% CAS versus 3% CEA). The power of the non-inferiority test is 80% in case of a slightly reduced risk in both procedures (CAS and CEA 2%).

Efficacy: In order to control the overall Type I error on the 5% level, a hierarchical testing procedure will be used. The first step of the procedure consists in a closed testing procedure for the difference between the three treatments. The tests are performed on a 5% level. If there are simultaneously significant differences between the pairs BMT and CEA as well as BMT and CAS on a 5% level, the hierarchical testing procedure enters step 2, otherwise there is no further statistical testing. Since superiority for CEA and CAS over BMT is not yet established in the studied population both tests need to be significant to allow the interpretation of step 2 in a clinically sensible way. Step 2 of the procedure consists in a non-inferiority test: The one-sided 97.5% confidence interval for the difference of the event rates (rate in the CAS group – the rate in the CEA group) will be calculated. Non-inferiority is proven if the upper margin of this interval is less than 2.5%.

In case of losses to follow up, the event rates and their standard errors will be calculated by Kaplan-Meier-techniques.

NEW:

Safety: If in the interim analysis the absolute rate of safety events (any stroke or death within 30 days after intervention) in the CEA-arm (for SPACE2a) or in the CAS-arm (for SPACE2b) with a confidence interval of 80% is higher than 3%, the DSMB can recommend stopping the trial. If the lower 80%-confidence-interval of the safety-event-rate is higher than 5%, the DSMB will recommend stopping the trial.

Efficacy: The primary analysis consists in testing the difference between BMT and intervention (CEA or CAS) with respect to the composite primary end point (Section 2.3) for each of the individuals substudies. The comparison will use the Cox-PH model. An explorative comparison of the event rates in the CEA and the CAS groups will be done (Calculating a 95% confidence interval of the hazard rate for the primary endpoint between both treatments). In order to analyze the effect between the two interventional methods, an indirect treatment comparison will be performed [17].

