1.1.3 Role of carotid endarterectomy

The Asymptomatic Carotid Surgery Trial (ACST) and the smaller Asymptomatic Carotid Atherosclerosis Study (ACAS) studied the role of CEA in nearly 5,000 patients with asymptomatic carotid stenoses (no stroke or stroke-like symptoms within the previous 6 months) [7-8]. A recent metaanalysis included three trials with a total of 5,223 patients. In these trials, the overall risk of perioperative stroke or death was 2.9%. For the

outcome of perioperative stroke or death or any subsequent stroke, patients undergoing CEA fared better than those treated medically (relative risk (RR) 0.69, 95% confidence interval (CI) 0.57 to 0.83). Similarly, for the outcome of perioperative stroke or death or subsequent ipsilateral stroke, there was benefit for the surgical group (RR 0.71, 95% CI 0.55 to 0.90). For the outcome of any stroke or death, there was a non-significant trend towards fewer events in the surgical group (RR 0.92, 95% CI 0.83 to 1.02)[4]. The general applicability of these findings has been questioned because morbidity and mortality rates exceeding 3% have been reported in general surgical practice under non-trial.

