4 SELECTION OF SUBJECTS

4.1 Number of subjects

OLD: As calculated in section 9.1 'Sample Size Calculation', 3,640 subjects should be enrolled in the clinical trial, 540 to the BMT-Arm, 1,550 to the surgical and 1,550 to the stenting-group.

NEW: As calculated in section 9.1 'Sample Size Calculation', 1636 subjects should be enrolled in the group sequential clinical trial with one interim analysis, 818 patients per arm. This is the case for SPACE2a comparing CEA with BMT and for SPACE2b comparing CAS with BMT. Both trials would require a total of 3,272 patients.

Recruitment and treatment of subjects should be performed in around 100 trial centers. The minimum / maximum number of subjects per trial centre should be 10/200.

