4.5.3 Premature Closure of the Clinical Trial

If the 30-day complication rate (any stroke or death) of one or both treatment modalities exceeds 3% (with an 80% confidence interval), the Data Safety and Monitoring Board (DSMB, see chapter 0) can give a recommendation to the steering committee to stop the trial. If the complication rate exceeds 5%, the DSMB will recommend stopping the trial.

The trial can be prematurely closed or suspended by the Executive Committee in case of new data about the risk-benefit of one of the treatment regimes becomes available or if the DSMB recommends study closure. The Ethics Committee (EC) and the competent regulatory authorities must then be informed. Furthermore, the Ethics Committee(s) and competent regulatory authorities themselves may decide to stop or suspend the trial.

Should the trial be closed prematurely, all trial material must be returned to the Coordinating Clinical Centre (Department of Neurology, University of Heidelberg)

All involved investigators have to be informed immediately about a cessation/ suspension of the trial. The decision is binding to all trial centers and investigators.

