9.5 Interim analyses

OLD: No interim analysis is planned with respect to the primary endpoint. An interim analysis of the safety data is planned after three years. This will not influence the sample size calculation because this is based on the efficacy endpoint. In addition the safety committee will check the safety regularly.

NEW: One interim analysis is planned with respect to the primary endpoint after five years. An interim analysis of the safety data is planned after three years. This will not influence the sample size calculation, because this is based on the efficacy endpoint. In addition the safety committee will check the safety regularly.

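### The mandatory 5% tier of the 30-day safety stopping rule has two different triggers: a rate above 5% in section 4.5.3, a lower 80% confidence limit above 5% in section 9.4 NEW

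*Protocol*

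**What the plan says.** The protocol has a two-tier rule on any stroke or death within 30 days in the intervention arm. The lower tier (3%) lets the DSMB recommend stopping; the upper tier (5%) commits it to doing so. The rule appears twice.

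- **Section 4.5.3** has no OLD or NEW mark, so it is current. Its lower tier applies when the rate "exceeds 3% (with an 80% confidence interval" attached. Its upper tier reads: "If the complication rate exceeds 5%, the DSMB will recommend stopping the trial". No interval appears in that sentence.
- **Section 9.4 (NEW, Safety)** has as its lower tier a rate which "with a confidence interval of 80% is higher than 3%, the DSMB can recommend stopping the trial". Its upper tier reads: "If the lower 80%-confidence-interval of the safety-event-rate is higher than 5%, the DSMB will recommend stopping the trial".

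On timing, section 9.5 (NEW) says "An interim analysis of the safety data is planned after three years" and adds "In addition the safety committee will check the safety regularly". Section 4.5.3 ties its rule to no particular look.

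**The concern.** Both upper tiers concern the same outcome, use the same 5% threshold, address the same body and lead to the same commitment. One compares the rate itself with 5%, the other its lower confidence limit. The limit lies below the rate, so section 4.5.3 is met first, and for a band of results it commits the DSMB while section 9.4 does not.

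This is the patient-protection rule for an invasive procedure in people without symptoms. In that band, a DSMB that lets the trial continue acts within section 9.4 but against section 4.5.3 as written. Which section governs would then be argued after the data had been seen.

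**Working it through.** The protocol gives no event counts or operating characteristics for this rule, so there is no stated figure to reproduce. The check asks where the two triggers part and how often.

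**Inputs**
- Arm size: "818 patients per arm" (section 4.1 NEW).
- Safety look at three years (section 9.5 NEW); accrual over 5 years (section 9.1 NEW, group sequential design).
- Assumed number treated at the look, with uniform accrual: 818 × 3/5 = 490.8, taken as n = 491. Alternatives: n = 409 (half the arm) and n = 818 (the whole arm, the upper bound if recruitment took the 3 years given in the summary).
- The interval method and the sidedness of the 80% limit are not stated, so Clopper-Pearson, Wilson and Wald limits were each tried one-sided and two-sided.

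**Step 1: event counts at n = 491**
- Section 4.5.3: smallest x with x/n > 0.05. 24/491 = 4.89% and 25/491 = 5.09%, so x = 25.
- Section 9.4: smallest x with lower limit > 0.05. The Clopper-Pearson limit is the α quantile of Beta(x, n − x + 1), with α = 0.10 for a two-sided and 0.20 for a one-sided 80% limit.
  - Two-sided: 32 (Clopper-Pearson, Wald) or 31 (Wilson). For Clopper-Pearson, x = 31 gives 4.94% and x = 32 gives 5.12%.
  - One-sided: 30 (Clopper-Pearson) or 29 (Wilson, Wald).
- The disputed band therefore runs from 25 events up to 28–31, an observed rate of 5.1% up to 5.7–6.3%.

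**Step 2: other numbers treated**

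| n | 4.5.3 met from | 9.4 met from | Disputed band |
|---|---|---|---|
| 409 | 21 | 25–27 | 21 up to 24–26 |
| 491 | 25 | 29–32 | 25 up to 28–31 |
| 818 | 41 | 47–50 | 41 up to 46–49 |

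**Step 3: chance of disagreement at one look.** This is P(X ≥ a) − P(X ≥ b), with X binomial(n, p), a the count for 4.5.3 and b the count for 9.4. At n = 491 and p = 5% with the two-sided exact limit: 0.492 − 0.079 = 0.413. With b = 29: 0.492 − 0.204 = 0.288.

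| True 30-day rate | Disagreement, n = 491 |
|---|---|
| 2.9% | 0.5% |
| 4% | 11–13% |
| 5% | 29–41% |
| 6% | 26–49% |
| 7% | 11–28% |

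The 2.9% row is the pooled surgical figure in section 1.1.3 ("the overall risk of perioperative stroke or death was 2.9" per cent). At n = 409 the chance is 0.9% at 2.9%, 30–39% at 5% and 31–47% at 6%. At n = 818 it is under 0.1%, 33–43% and 26–43%.

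**Step 4: is the 3% tier already met?** A lower 80% limit above 3% needs 18–21 events at n = 491, 16–18 at n = 409 and 29–32 at n = 818. Each lies below the start of the disputed band, so throughout it the DSMB may recommend stopping under either section.

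**Step 5: the regular checks, with 50 treated as an example.** 3/50 = 6%, so three events meet the 5% tier of 4.5.3. At a true 3%, P(X ≥ 3) = 18.9%. The two-sided Clopper-Pearson limit passes 5% only at six events, with P(X ≥ 6) = 0.4%. The two-sided 3% tier needs four events here, so the tier that commits the DSMB could be met before the one that merely permits.

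**The case against.** The strongest defence is that the interval in the 3% sentence of section 4.5.3 sets the convention for the whole rule. The 5% sentence would then be its second step, and section 9.4 merely spells it out. That reading is plausible and would remove the conflict. But section 4.5.3 attaches the interval to one sentence and omits it from the next, and someone applying that section alone would use the plain rate. If the carry-over was intended, section 4.5.3 still needs the words.

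A reader might infer that the DSMB would be in breach whatever it did. The documents do not support that. Section 9.4 says when a recommendation will follow; it does not say that none may follow otherwise. At the sizes examined the 3% tier is already met, so recommending a stop satisfies both sections. Only declining to recommend is in conflict, and only with section 4.5.3.

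A reader might also count the unstated interval method and sidedness as defects. They can be settled in the SAP, which was not available here; they only widen the range of the figures above.

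Other points in defence stand. Both tiers produce a recommendation, not an automatic stop. Disagreement is rare if the true rate is near 2.9%. Section 10.1, on the DSMB, was not available and might say more, although sections 4.5.3 and 9.4 would still differ from each other.

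**Conclusion.** The point holds as an inconsistency in a stated decision threshold: the protocol is wrong as written, because its upper safety tier has two triggers in current text. At an assumed 491 treated they part from 25 events up to 28–31, and a gap is present at every size examined. The practical consequence is limited to whether the DSMB must or may recommend stopping. That question is unlikely to arise at a true rate near 2.9% (about 0.5% of looks). At true rates of 5% to 6%, where the upper tier is meant to work, it arises in roughly a quarter to a half of looks.

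These figures assume a single look, binomial counts and uniform accrual for n = 491, and a literal reading of section 4.5.3. The difference in wording is certain; a difference in intent is not. The point is worth correcting because the rule protects patients and the correction is small.

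**What to change.** State one trigger for the 5% tier, word for word the same in sections 4.5.3 and 9.4. The amended 9.4 wording (lower 80% limit above 5%) is the natural candidate: it is explicit, and it avoids a mandatory recommendation on very few patients at the regular checks. Interval method and sidedness can be fixed in the SAP.

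The DSMB and steering committee should confirm that choice, or adopt the stricter plain-rate trigger in both places, because the 9.4 wording is less protective. At n = 491 with the two-sided exact limit, the mandatory tier is met as follows:

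| True rate | Lower limit above 5% | Rate above 5% |
|---|---|---|
| 4% | 0.5% of looks | 13% |
| 5% | 8% | 49% |
| 6% | 34% | 83% |
| 7% | 69% | 96% |

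Under the 9.4 wording the discretionary 3% tier remains available; by the same limit (21 events) it is met in 80%, 96% and over 99% of looks at 5%, 6% and 7%.

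The cost is one sentence in each section, with no extra patients, visits or procedures. If the change counts as substantial, section 11.5 requires an amendment approved by the ethics committee.

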9.5 Interim analyses

OLD: No interim analysis is planned with respect to the primary endpoint. An interim analysis of the safety data is planned after three years. This will not influence the sample size calculation because this is based on the efficacy endpoint. In addition the safety committee will check the safety regularly.

NEW: One interim analysis is planned with respect to the primary endpoint after five years. An interim analysis of the safety data is planned after three years. This will not influence the sample size calculation, because this is based on the efficacy endpoint. In addition the safety committee will check the safety regularly.

10.5 Control of treatment quality

10.5.1 Centers

Each study center must consist of at least one neurologist, one vascular surgeon and one endovascular therapist. Clinics which lack of one of these components may join other centers. Certification of a participating center will follow upon compliance to all quality criteria. The steering committee or the executive committee can withdraw the certification to participate in the trial on recommendation of the DSMB and or the monitoring agency.

10.5.2 Investigators

For all involved disciplines quality criteria are defined by the appropriate quality committee (see Appendix). Every neurologist has to demonstrate his/her ultrasound-expertise and must have a NIHSS-certificate. Vascular surgeons and interventionalists must demonstrate at least 30 consecutive procedures with mortality and morbidity rates of these procedures. The local principal investigator has to confirm this documentation. Together with the DSMB the quality committees will monitor local complication rates and can recommend the steering-committee or the executive committee to withdraw a certificate.

10.6 Participating sites

The appendix will contain an extra document listing all participating sites.

11 ETHICAL AND LEGAL ASPECTS

11.1 Good Clinical Practice

The procedures set out in this trial protocol, pertaining to the conduct, evaluation, and documentation of this trial, are designed to ensure that all persons involved in the trial abide by Good Clinical Practice (GCP) and the ethical principles described in the applicable version of the Declaration of Helsinki. The trial will be carried out in keeping with local legal and regulatory requirements.

11.2 Subject information and informed consent

Before being admitted to the clinical trial, the subject must consent to participate after the nature, scope, and possible consequences of the clinical trial have been explained in a form understandable to him or her. The subject must give consent in writing. The signed Informed Consent Form will be filed by the investigator.

A copy of the signed informed consent document must be given to the subject. The documents must be in a language understandable to the subject and must specify who informed the subject.

The subjects will be informed as soon as possible if new information may influence his/her decision to participate in the trial. The communication of this information should be documented.

11.3 Confidentiality

The data obtained in the course of the trial will be treated pursuant to the Federal Data Protection Law (Bundesdatenschutzgesetz, BDSG).

During the clinical trial, subjects will be identified solely by means of their initials, date of birth, and an individual identification code (subject number, randomization number). Trial findings stored on a computer will be stored in accordance with local data protection law and will be handled in strictest confidence. For protection of these data, organizational procedures are implemented to prevent distribution of data to unauthorized persons. The appropriate regulations of local data legislation will be fulfilled in its entirety.

The subject consents in writing to release the investigator from his/her professional discretion in so far as to allow inspection of original data for monitoring purposes by health authorities and authorized persons (inspectors, monitors, auditors). Authorized

persons (clinical monitors, auditors, inspectors) may inspect the subject-related data collected during the trial ensuring the data protection law.

The investigator will maintain a subject identification list (subject numbers with the corresponding subject names) to enable records to be identified.

Subjects who did not consent to circulate their pseudonymized data will not be included into the trial.

11.4 Responsibilities of investigator

The investigator should ensure that all persons assisting with the trial are adequately informed about the protocol, any amendments to the protocol, the trial treatments, and their trial-related duties and functions.

The investigator should maintain a list of subinvestigators and other appropriately qualified persons to whom he or she has delegated significant trial-related duties.

11.5 Approval of trial protocol and amendments

Before the start of the trial, the trial protocol, informed consent document, and any other appropriate documents will be submitted to the independent Ethics Committee (EC). A written favorable vote of the EC is a prerequisite for initiation of this clinical trial. The statement of EC should contain the title of the trial, the trial code, the trial site, and a list of reviewed documents. It must mention the date on which the decision was made and must be officially signed by a committee member. This documentation must also include a list of members of the EC present on the applicable EC meeting.

Before the first subject is enrolled in the trial, all ethical and legal requirements must be met. All planned substantial changes (see §10, (1) of German GCP-Regulation) will be submitted to EC in writing as protocol amendments. They have to be approved by the EC.

The investigator will keep a record of all communication with the EC and the regulatory authorities.

11.6 Continuous information to independent ethics committee

The EC will be informed in case the risk/ benefit assessment had changed or any others new and significant hazards for subjects' safety or welfare did occur. Furthermore, a report on all observed serious adverse events (SAEs) will be submitted once a year – Annual Safety Report. The EC and the regulatory authorities will be informed of the end

of the trial. They will be provided with a summary of trial results within one year after the end of clinical phase (LSO).

11.7 Registraton of the trial

Application has been filed to <http://www.controlled-trials.com>, the study code is ISRCTN 78592017. In addition the protocol of the study will be published in a peer-reviewed journal.

12 QUALITY ASSURANCE

12.1 Monitoring

The Monitoring will be performed by the Coordination Center for Clinical Trials (KKS) Heidelberg according to ICH-GCP (E6) and approved standard operating procedures of the KKS to ensure patients safety and integrity of the clinical data in adherence to study protocol. Prior to study start all participating centers will be trained and introduced into all study specific procedures by central initiations. Regular on-site monitoring visits are planned at all sites (approximately 9-10 on-site visits per center depending on the recruitment rate and quality of the data). Source data verification of predefined core and safety data will be done for all included subjects. For at least 10% of all subjects a 100% source data verification (SDV) for all items is planned. The extend of 100% SDV or the frequency of monitoring-visits will be increased for individual centers in case bad quality of data or common protocol violations are observed. In return frequency of monitoring visits can be reduced for reliable and compliant centers with high data quality. Queries of the data management (e.g. in case of missing values, implausibility etc.) have to be answered by the investigators contemporary to avoid that errors in data capture or entry will be carried forward. In addition to the SOPs all procedures are described in a study-specific monitoring-manual.

12.2 Inspections / Audits

Regulatory authorities and an auditor authorized by the sponsor may request access to all source documents, CRF, and other trial documentation. Direct access to these documents must be guaranteed by the investigator who must provide support at all times for these activities.

13 AGREEMENTS

13.1 Financing of the trial

The trial will be financed using funds of the BMBF and DFG (HA 1394/5-1). Co-financing by pharmaceutical industry and stent manufactures will be arranged.

13.2 Publication

All information concerning the trial is confidential before publication. The safety (30-day) results will be published first. Final results will be published after end of the trial. Publications will be prepared from a writing committee in the name of all SPACE-2 investigators.

17 APPENDICES

Declaration of Helsinki (applicable Version)

List of participating centres

Standard procedures of the 'Best Medical Treatment' subgroup

Standard procedures of the 'Neurology' subgroup

Standard procedures of the 'Vascular surgery' subgroup

Standard procedures of the 'Endovascular Treatment' subgroup
